8.1 Reporting Adverse Events

All serious adverse events (SAEs) that occur from the start of study drug through thirty days after the last dose of study medication must be reported or if the patient is pregnant, 6 weeks following delivery. A serious adverse event is defined as: fatal or immediately life-threatening; severely or permanently disabling; requiring or prolonging inpatient hospitalization; overdose (intentional or accidental); congenital anomaly; pregnancy loss after 20-weeks gestation; neonatal death up to 6 weeks after delivery; or, any event adversely affecting the study's risk/benefit ratio. Additionally, any event that, based on appropriate medical judgment, may jeopardize the subject's health and may require medical or surgical intervention to prevent one of the outcomes listed above is considered an SAE.

If an SAE occurs and is thought to be related to the study medication, the study medication will be discontinued. Twenty-four hour unblinding will be available through the web-based randomization system to break the randomization code for the individual patient if this is required by the PI for proper treatment of the patient.

The site PI will report the SAE by completing and signing the Serious Adverse Event Report Form [available in the "Study Forms" section of the RMN members-only website], and then emailing the document in PDF format to [contact]. Subjects will be identified by study number only. No other identifying information will be included on the form. The site PI must determine and record on the SAE form whether the SAE is unanticipated or anticipated, and if it is related, possibly related, or unrelated to participation in the research.

DCC staff will enter the SAE information in the central database. The Safety Surveillance team, consisting of the DCC, NICHD research scientist and lead PI of the protocol, will analyze the SAE to determine if it meets the criteria listed in the OHRP 45CFR46 and/or FDA 21CFR312.32 & 3.14.80.

These determinations will dictate timeframes for sites' submission to the DCC, and the DCC's submission to the DSMB:

Upon receiving notification of an SAE, the DSMB will review it via a closed-session email or conference-call discussion arranged by the NICHD RMN Committee Coordinator (RMN CC). The DSMB will send a report to the RMN CC within two weeks; reports for life-threatening SAEs will be submitted in one week. The DSMB report will include: statement indicating what related information the DSMB reviewed; the review date; the DSMB's assessment of the information reviewed; and the DSMB's recommendation, if any, for the DCC.

[figure not shown]
Table 4: Types of Serious Adverse Events and Their Reporting Requirements

TYPE	SITE	DCC
Unanticipated and related/possibly related SAE, fatal or life-threatening	Report to DCC within 1 business day of discovery	Notify DSMB by end of next business day of receiving site report
Other unanticipated and related/possibly related SAE	Report to DCC within 1 business day of discovery	Notify DSMB 5 business days of receiving site report
Anticipated and related/possibly related SAE	Report to DCC within 5 business days of discovery	Notify DSMB 5 business days of receiving site report
Unrelated SAE (anticipated or unanticipated)	Report to DCC within 10 business days (no more than 3 weeks) of discovery	Notify DSMB within 10 business days (no more than 3 weeks) of receiving site report

The RMN CC will then forward the DSMB report to the DCC for the record and appropriate distribution. The DCC will forward reportable events to all RMN investigators, NICHD, and the FDA on behalf of the NICHD if the protocol is under IND. The NICHD Project Scientist will review, sign, and return the IND safety report to the DCC within 2 business days, and will follow up with the site PI and DCC on the SAE until it is resolved. The Protocol PI will evaluate the frequency and severity of the SAEs and determine if modifications to the protocol and consent form are required. Site PIs will report the SAE to their site IRB according to local IRB requirements. For more information, please see the RMN/DSMB Communication Procedure.

Adverse events deemed non-serious will also be recorded throughout study participation from the start of study drug through one week after the last dose of study medication, and reported to the DCC. If an anticipated serious adverse event occurs at a frequency greater than expected, the DCC will notify the DSMB by the end of the next business day of discovery and follow the procedures for reporting serious and unanticipated and related adverse events. The DCC will forward relevant safety information to the DSMB. If an adverse event not initially determined to be reportable to the FDA under 21CFR312.32 is so reportable, the DCC will report the adverse event to the FDA within 15 calendar days after the determination is made. A flow chart for SAEs follows:

Figure 2: SAE flowchart

CFR= Code of Federal Regulations

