7.2 Primary and Secondary Outcomes

The primary outcome is a live birth resulting from a pregnancy occurring within the 6 months of treatment. Live birth is defined as a delivery of a live infant after 20-weeks gestation. Secondary outcomes include pregnancy, defined by a positive home pregnancy test within the 6 months of treatment. We will conduct an intent-to-treat analysis. Cumulative incidence of live birth and pregnancy will be compared between those couples randomized to antioxidants and those couples randomized to placebo. In addition, discrete-time hazard models will be used to compare time-to-pregnancy between groups. Subsequent subgroup analyses will be conducted to assess for effect modification by type of baseline sperm abnormality. All analyses will include fixed or random effect terms as needed to account for potential site effects.

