7.3 Sample Size and Statistical Power

For the power analysis, we assume live birth rates of 35% in the antioxidant group and 25% in the control group, and 17% drop-out (based on drop-out rate in prior RMN trials). A 25% live birth rate was estimated, assuming 5% live birth rate in the first 3 months of timed intercourse and a 20% live birth rate in the 3 clomid/IUI cycles. The 20% live birth rate is the live birth rate in AMIGOS participants receiving up to 3 cycles of clomid/IUI and female partner under the age of 35. Under these assumptions, a sample size of 395 per group will yield 80% power using a two-sided chi square test at $\alpha=0.05$ (Table 2).

Table 2: Sample size estimates under a variety of assumptions

Proportion (%) of live birth in placebo group	Proportion (%) of live birth in antioxidant group	Power (%)	Number of patients per arm with 0% dropout	Total number of patients with 0% dropout	Total number of patients with 17% dropout
20	30	80	294	588	708
20	30	90	392	784	944
25	35	80	328	656	790
25	35	90	440	880	1060
30	40	80	356	712	858
30	40	90	477	954	1150
20	35	80	138	276	332
20	35	90	185	370	446
25	40	80	152	304	366
25	40	90	203	406	490

For subgroup analyses, power is dependent on the distribution of the sperm abnormalities, the control live birth rate and the treatment effect difference (see Table 3).

Table 3: Power for subgroup analyses

Proportion affected (%)	Total N for subgroup	Control Group Pregnancy Proportion (%)	Treatment Effect Difference (%)	Alpha	Power (%)
70	552	20	10	0.05	78
60	474	20	10	0.05	71
50	394	20	10	0.05	63
40	316	20	10	0.05	54
30	236	20	10	0.05	43
70	553	20	15	0.05	98
60	474	20	15	0.05	96
50	395	20	15	0.05	92
40	316	20	15	0.05	85
30	237	20	15	0.05	74
70	553	25	15	0.05	97

60	474	25	15	0.05	94
50	395	25	15	0.05	89
40	316	25	15	0.05	82
30	237	25	15	0.05	69

8 Technical Aspects

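### Section 8.1 does not say whether admission for an uncomplicated delivery is an SAE, and SAE frequency per randomised couple would rise with efficacy whichever way sites read it

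*Combined protocol and SAP*

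**What the plan says.** Section 8.1 (Reporting Adverse Events) defines seriousness by a list. After fatal, life-threatening and disabling events it continues: "requiring or prolonging inpatient hospitalization; overdose (intentional or accidental); congenital anomaly; pregnancy loss after 20-weeks gestation; neonatal death up to 6 weeks after delivery". The hospitalization item carries no qualifier. SAEs are reportable from the start of study drug to thirty days after the last dose, "or if the patient is pregnant, 6 weeks following delivery", so the female partner's whole pregnancy and delivery fall inside the window.

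Table 4 sorts SAEs by whether they were anticipated and related. That sets the reporting deadlines, but every class, including unrelated SAEs, is sent to the DSMB. The text adds: "Upon receiving notification of an SAE, the DSMB will review it via a closed-session email or conference-call discussion". A DSMB report follows within two weeks, or one week if the event is life-threatening. Section 8.1 also escalates anticipated SAEs that occur more often than expected, without giving an expected frequency.

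Section 7.2 states: "The primary outcome is a live birth resulting from a pregnancy occurring within the 6 months of treatment", and "Live birth is defined as a delivery of a live infant after 20-weeks gestation". Sections 5.7.9 and 6.10 collect delivery details and obstetrical complications as pregnancy outcome data.

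The DSMB charter (Appendix T, Report Schedule and Content) lists SAEs among the contents of both brief and full reports. It does not separate SAEs that depend on pregnancy from the rest.

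**The concern.** A safety count is hard to interpret when the same event can be both the treatment's intended benefit and a reportable harm. If a site follows the wording of 8.1, each hospital delivery produces an SAE form and an individual DSMB review. If another site decides that a normal delivery is not adverse, it files nothing. SAE totals would then depend on local interpretation.

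The list also names congenital anomaly, pregnancy loss after 20 weeks and neonatal death. None of these can occur in a couple who do not conceive. The longer window applies only to couples who do. An arm with more pregnancies therefore has more couples at risk of these events and more observed time per couple, even if treatment has no effect on harm. At stake is whether the DSMB and the final report can tell a safety difference from a consequence of efficacy.

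**Working it through.** **Inputs from the plan.** From section 7.3: "we assume live birth rates of 35% in the antioxidant group and 25% in the control group, and 17% drop-out", and "a sample size of 395 per group will yield 80% power", with a two-sided chi-square test at 0.05. Table 2 gives 328 per arm before dropout.

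**Reproducing the plan's figure.** With pooled variance and no continuity correction, and mean proportion 0.30:

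n = [1.960 × √(2 × 0.30 × 0.70) + 0.842 × √(0.35 × 0.65 + 0.25 × 0.75)]² / 0.10² ≈ 329 per arm (stated 328).

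Power at 328 per arm is 79.9%. Dropout inflation gives 656 / 0.83 = 790.4 (stated 790). The planning rates and sample size agree with each other.

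**Case A: sites report every delivery admission.** Assume one admission per couple with a live birth and all deliveries inpatient. Expected SAEs from delivery = live birth rate × couples per arm.

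| Couples per arm | Antioxidant | Placebo | Excess | Ratio |
|---|---|---|---|---|
| 395 (randomised) | 395 × 0.35 = 138.3 | 395 × 0.25 = 98.8 | 39.5 | 1.4 |
| 328 (after dropout) | 328 × 0.35 = 114.8 | 328 × 0.25 = 82.0 | 32.8 | 1.4 |

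The plan does not give the share of deliveries in hospital. At an assumed 90%, the counts are 124 vs 89 of 395.

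**Adding other SAEs.** Suppose a proportion b of couples in each arm also has an SAE independent of delivery (assumption: b = 1% to 10%). The proportion with any SAE is 1 − (1 − live birth rate)(1 − b).

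- b = 1%: 35.7% vs 25.8%, ratio 1.38.
- b = 10%: 41.5% vs 32.5%, ratio 1.28.

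The plan specifies no between-arm test of SAEs. As a gauge of visibility only, a two-sided 0.05 comparison would flag the difference 80% (328 per arm) to 87% (395 per arm) of the time at b = 0, and 67% to 75% at b = 10%.

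**Case B: no routine delivery is reported.** Suppose a share c of delivering couples has a pregnancy-dependent SAE, equal in both arms (assumption: c = 5% to 30%; the plan gives no rate).

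| c | Antioxidant, per couple | Placebo, per couple | Couples of 395 | Chance of being flagged |
|---|---|---|---|---|
| 5% | 0.35 × 0.05 = 1.75% | 0.25 × 0.05 = 1.25% | 6.9 vs 4.9 | 8% |
| 30% | 0.35 × 0.30 = 10.5% | 0.25 × 0.30 = 7.5% | 41 vs 30 | 31% |

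The per-couple ratio remains 0.35c / 0.25c = 1.4. Per delivery it is c / c = 1.0. Excluding routine deliveries shrinks the absolute imbalance; a pregnancy or delivery denominator removes what remains in this calculation. The longer window acts in the same direction but cannot be sized from the plan.

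**The case against.** A reader might infer that under this plan every hospital delivery is an SAE and that the antioxidant arm will therefore look less safe. The documents do not support that.

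- The list in 8.1 sits under a heading about adverse events, and delivery of a live infant is the intended outcome. Sections 5.7.9 and 6.10 give delivery its own route as a pregnancy outcome, with complications recorded separately. The pregnancy events that 8.1 names are all adverse ones. Nowhere does the plan state that a delivery is an SAE.
- No between-arm SAE comparison is planned. DSMB summaries are blinded by default, and both report types carry an update on the primary outcome, so live births would be in view beside SAEs.
- Classification speeds up what matters. An unanticipated, related SAE reaches the data coordinating center within 1 business day and an unrelated one within 10, so it would be too strong to say that genuine signals are buried.
- An exemption may exist in the SAE flowchart, SAE form, consent pages or operating procedures, none of which is in the supplied text.

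All of this stands against the stronger reading. It does not close the gap. Classification changes deadlines, not whether an event is counted. Two reasonable readings of 8.1 invite inconsistent reporting. A live birth update in the report is not the same as tabulating SAEs against pregnancies. Nothing here touches the events that can occur only in pregnancy, or the longer window.

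**Conclusion.** The point holds in a limited form. Section 8.1 read literally covers admission for uncomplicated delivery, and the supplied text neither confirms nor exempts it. If sites report these admissions, all deliveries are inpatient and the planning effect is real, delivery adds about 138 vs 99 SAEs per 395 couples, or 115 vs 82 per 328: an excess of 33 to 40 at a ratio of 1.4. If any of those conditions fails, the figures change, and with no effect on live birth there is no systematic imbalance from this source.

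The firmer part does not depend on site practice. Pregnancy-only SAEs and a window extended only for pregnant participants make SAE frequency per randomised couple follow efficacy. Stopping enrolment after the internal pilot would reduce the counts but leave the mechanism.

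This is a cheap improvement rather than a flaw that threatens the trial. Confidence is medium because of the SAE material that could not be seen.

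**What to change.** In section 8.1 and the SAE form instructions, state that admission for an uncomplicated delivery is recorded as a pregnancy outcome and not as an SAE, and that an admission caused or prolonged by a complication remains an SAE. If such an exemption already exists elsewhere, repeat it in 8.1.

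In the DSMB reports and the final safety tables, show pregnancy-dependent SAEs separately from those that can occur in any participant. Give them per pregnancy and per delivery as well as per randomised couple.

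The cost is one sentence and an added set of denominators, from data the trial already collects. Treatment and follow-up are unchanged. The small downside is that sites must judge whether an admission was for a complication.

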8.2 Data Collection and Management (including quality assurance/compliance measures)

8.2.1 *Data Entry and Forms*

Case Report Forms (CRFs) will be developed as the protocol is developed. They will also be implemented in a Web-based Oracle data management system. The Web data entry forms will be similar to the paper forms with the same questions. However, the Web forms usually have more flexibility than the paper forms, such as pull-down menus.

8.2.2 *Features of Data Management System*

Features of the data management system include study definition; different types of data entry (including double entries and complete audit trail); forms control; query capture, reporting, and resolution; dictionary coding of Adverse Events (AEs) and medical terms; and clinical data review Tools; and prepares data and CRF images to FDA e-Submission Standards. The end-user/reporting/ad hoc query front-end uses a standard Web browser, so that data entry and browsing can be done from any machine with Internet access, without purchase of special software. Login to this system will be through a secured Web server with the security under the protection of Yale Center for Clinical Investigations.

8.2.3 *Data Security*

A data server and Web server will be used. The data server will be managed by YNHH IT center and the website two servers will be separated and managed by Forte Research Systems. The web server will be accessible through a secured login, but the data server can only be accessed through the web server. For security purposes, no login to the data server will be permitted, and access to the back end is limited to authorized individuals. PHI, including patient names and addresses, will be locked and secured at the participating sites, and data will be linked through a unique identification number, which will be assigned after a patient is screened or enrolled. Access will be limited to authorized individuals (21 CFR 11.10(d)). Each user of the system will have an individual account. The user will log into the account at the beginning of a data entry session, input information (include changes) on the electronic record, and log out at the completion of the data entry session. The system will be designed to limit the number of log-in attempts and record unauthorized access log-in attempts. Individuals will work only under their own access key, and not share these with others. The system will not allow an individual to log onto the system to provide another person access to the system. Access key Users will be asked to change their passwords at established intervals commensurate with a documented risk assessment. This plan has been adapted from the guidelines for computerized systems used in clinical investigations established by the U.S. Department of Health and Human Services Food and Drug Administration.

8.2.4 *Data Quality Control*

Competency to perform procedure/tests in the protocol

The site PI will be responsible for ensuring that study related tests are performed by competent personnel. The criteria for determination of competency may vary between sites in the study.

Attempts will be made to standardize operating procedures whenever possible to minimize inter-site variation.

Quality Control Steps

Quality control of data will be handled on three different levels. The first level is the real-time logical and range checking built into the web-based data entry system. The research coordinators and data entry clerks at the participating sites are required to ensure the data accuracy as the first defense. The second is the remote data monitoring and validation that is the primary responsibility of the data manager and programmer at the DCC. The data manager will conduct monthly comprehensive data checks (SAS programs run on a regular basis as a systematic search for common errors and omissions), as well as regular manual checks (within the database system). Manual checks will identify more complicated and less common errors. The data manager will query sites until each irregularity is resolved. The third level of quality control will be the site visits, where data in our database will be compared against source documents. Identified errors will be resolved between our center and clinical sites. The visits will assure data quality and patient protection.

An audit trail will be added as another security measure. This will ensure that only authorized additions, deletions, or alterations of information in the electronic record have occurred and allows a means to reconstruct significant details about study conduct and source data collection necessary to verify the quality and integrity of data. Computer generated, time-stamped audit trails will be implemented for tracking changes to electronic source documentation.

Controls will be established to ensure that the system's date and time are correct. This is a multi-center clinical trial and will be located in different time zones. System documentation will explain time zone references as well as zone acronyms. Dates and times will include the year, month, day, hour, and minute to the date provided by international standard-setting agencies (e.g. US National Institute of Standards and Technology). The ability to change the date or time will be limited to authorized personnel, and such personnel will be notified if a system date or time discrepancy is detected.

In addition to internal safeguards built into the computerized system, external safeguards will be implemented. Data will be stored at the Data Coordination Center. Records will be regularly backed up, and record logs maintained to prevent a catastrophic loss and ensure the quality and integrity of the data. This plan has been adapted from the guidelines for computerized systems used in clinical investigations established by the U.S Department of Health and Human Services Food and Drug Administration.

8.3 Study Monitoring

A monitoring plan that satisfies ICH/GCP guidelines for monitoring clinical trials will be used. A Project Manager from the DCC will lead this effort, and report findings to the DCC PI. The Project Manager will have full knowledge of the study protocol, Manuals of Procedures, and is familiar with the database system and is trained to review patient charts. The Project Manager will be responsible for training and supervising other personnel.

Once personnel at participating site are trained to recruit patients, the Project Manager will be sent to the site to help initiate the study according to the study protocol, and to ensure that the clinical site meets the scientific, clinical, and regulatory requirements. For example, the Project Manager will review all signed and dated forms required by the FDA (such as financial disclosure forms), the curriculum vitae and certifications of the investigators and personnel, CRF training, and the written IRB approval of the protocol and consent form.

The on-site monitor will return to the clinical site after a defined number of patients are recruited (can be as early as the recruitment of the 2nd patient) or a certain time period has passed, depending on the duration of the protocol execution. The schedule of visits will be discussed and agreed in the Steering Committee and we anticipate that the Project Manager will visit each participating site at least once.

During the site visit, the clinical sites should provide to the monitor a space and access to all relevant records including medical records and regulatory binders, and there would be immediate verbal feedback provided to the site after original source documents are compared to entries in the CRF. The clinical sites must agree to cooperate with the monitor to ensure that any problems detected in the course of these monitoring visits are resolved. The on-site monitor will conduct an audit of a random sample of entered information against the source documents, a review of all regulatory documents, a review of all informed consents, and a review of all pharmacy logs. The clinical site PI and coordinator should be available to meet the monitor during the visit. The monitor will review electronic data from all sites, providing a method for identifying systematic errors or problems.

To assure Good Clinical/Laboratory Practice, the monitor will control adherence to the protocol at the clinical sites and evaluate the competence of the personnel at the clinical sites including the ability to obtain written informed consents and record data correctly. The monitor will inform the DCC PI, the Steering Committee, and NICHD regarding problems relating to facilities, technical equipment, or medical staff. A thorough written report will follow each site-visit and will include a detailed itemization of discrepancies and items requiring follow-up or reconciliation. This report will also be forwarded to the NICHD Research Scientist for review. The monitor will be responsible for maintaining regular contacts between the investigators in the clinical sites and the RMN. When the study ends, the monitor will also visit the clinical site to provide assistance for close-out.

